3.7.6 Pharmacokinetic Assessments

Plasma concentrations of brexpiprazole will be analyzed using validated highperformance liquid chromatography-tandem mass spectrometry. Additional metabolites that are not identified in the protocol may also be analyzed if new information becomes available. If the need arises, plasma may be used in the study of analysis methods.

The bioanalytical laboratory will submit the results of drug concentration measurement in the form of an electronic file to the sponsor. It is therefore not necessary to record the measurement results on the source documents and eCRF.

3.7.6.1 Time Points for Blood Sampling

3.7.6.1.1 Brexpiprazole Conventional Tablet

In Period 1 of both the single administration period (Cohort 1 and Cohort 1' [as necessary]) and the repeated administration period (Cohort 2), blood samples after dosing of a conventional tablet will be collected at the time points shown in Table 3.7-1 and Table 3.7-2 or at withdrawal. Acceptable windows for blood sampling after dosing of a conventional tablet are shown in Table 3.7-3.

3.7.6.1.2 Brexpiprazole QW Formulation

In Periods 2 and 3 of the single administration period (Cohort 1 and Cohort 1' [as necessary]) and Period 2 of the repeated administration period (Cohort 2), blood samples after dosing of the QW formulation will be collected at the time points shown in Table 3.7-1 and Table 3.7-2 or at withdrawal. Acceptable windows for blood sampling after dosing of the QW formulation are shown in Table 3.7-4 to Table 3.7-6.

[Rationale for time points for blood sampling]

Time points for blood sampling for the conventional tablet were determined based on the following: A single oral dose trial (331-07-002), a multiple oral dose trial (331-10-001), a bioequivalence trial of oral solution (331-10-005), and a bioavailability trial of orally disintegrating tablets (331-102-00019) were conducted in Japan. After conventional tablets 2 mg and 4 mg were administered as a single dose, the median t_{max} for the unchanged drug was 6 hours, and the mean elimination half-life, which was determined at 3 to 8 time points between 36 to 312 hours postdose, was 52.9 to 72.7 hours. A total of 13 time points, namely, predose and 2, 4, 6, 8, 12, 24, 48, 72, 120, 168, 240, and 312 hours postdose, were set for blood sampling in Period 1 of both the single administration period (Cohort 1 and Cohort 1' [as necessary]) and the repeated administration period (Cohort 2) to cover the PK process from absorption to elimination, with reference to the results of the above 4 trials as well as "Partial Amendments to Guideline for Bioequivalence Studies of Generic Products (PFSB/ELD Notification No.0229-10 dated 29 Feb 2012)" (hereinafter referred to as "BE Guideline"), Section 3 Test, A. II. 1. 5) Measurement of biological samples, b. Sampling schedule.

Time points for blood sampling for the QW formulation were determined with reference to the PK data on the OROS formulation from a clinical pharmacology trial (Japan 331-102-00021) for comparative investigation of the PK, tolerability, and safety of 3 types of brexpiprazole QW formulation administered as single oral doses in patients with schizophrenia and with reference to the BE Guideline. A total of 11 time points, namely, predose and 3, 9, 24, 36, 48, 72, 120, 168, 240, and 312 hours postdose, were set for
blood sampling in Period 3 of the single administration period (Cohort 1 and Cohort 1' [as necessary]) and for the fifth administration in Period 2 of the repeated administration period (Cohort 2) to cover the PK process from absorption to elimination. For each of the first to fourth administrations of the QW formulation, 168 hours postdose, the time point of trough concentration, was set for blood sampling to ascertain if the plasma brexpiprazole concentration has reached the steady state. In addition, a total of 7 time points, namely, predose and 3, 9, 24, 36, 48, and 168 hours postdose, were set for blood sampling in Period 2 of the single administration period (Cohort 1 and Cohort 1' [as necessary] to obtain samples for use in estimation of parameters with a population PK analysis model.

3.7.6.2 Pharmacokinetic Plasma Samples

All plasma samples will be shipped to the bioanalytical laboratory. Detailed handling and shipping instructions are provided in Appendix 1.

3.7.7 CYP2D6 Genetic Testing

CYP2D6 genotype and phenotype will be analyzed. CYP2D6*1, *2, *4, *5, *10, *14, *18, *21, and *41 alleles will be analyzed. The CYP2D6 genotype will be determined for each subject based on the CYP2D6 genotyping table (Appendix 2). In addition, based on the CYP2D6 genotype, the phenotype will be classified into the following 4 types: extensive metabolizer (EM), intermediate metabolizer (IM), poor metabolizer (PM), and unknown. The results of CYP2D6 genetic testing will not, in principle, be disclosed to subjects

The genetic test laboratory will submit the results of CYP2D6 genetic testing in the form of an electronic file to the sponsor. It is therefore not necessary to record the test results on the source documents and eCRF.

3.7.7.1 Deoxyribonucleic Acid Blood Samples for CYP2D6 Genetic Testing

All blood samples will be shipped to the genetic test laboratory. Detailed handling and shipping instructions are provided in Appendix 1.

3.7.8 Future Biospecimen Research Samples

3.7.8.1 DNA Storage

3.7.8.1.1 Objective of DNA Storage

DNA storage will be conducted to enable future exploratory investigation regarding specific DNA mutations related to individual differences in responses to brexpiprazole

(efficacy, safety, or PK) and/or specific DNA mutations related to disease onset, severity, progression, etc.

3.7.8.1.2 Target Subjects of DNA Storage

Blood samples for DNA storage will be collected at the trial sites where DNA storage has been approved by the IRB. Only subjects from whom written informed consent for DNA storage has been obtained on a voluntary basis will be included (if the subject is a minor or hospitalized for reasons of medical protection, written consent must also be obtained from the subject's legal representative).

3.7.8.1.3 Blood Samples for DNA Storage

All blood samples will be shipped to the DNA storage facility. Detailed handling and shipping instructions are provided in Appendix 1. DNA samples will be stored until the earliest of the following time points: 1) when genomic/genetic analysis is judged to be unnecessary, 2) when 15 years have passed since receipt of informed consent for the first DNA storage, 3) when the subject withdraws consent to participate in DNA storage.

3.7.8.1.4 Genomic/Genetic Analysis

Genomic/genetic analysis will be performed only when considered useful for the purpose described in Section 3.7.8.1.1 Objective of DNA Storage.

If it is decided to perform genomic/genetic analysis, a pharmacogenomic research protocol will be prepared and the analysis will be carried out in compliance with the applicable local regulations to be followed when conducting analysis, after obtaining approval from the sponsor's IRB. The results will not be included in the clinical study report. A separate study report will be produced instead.

Target genes for genomic/genetic analysis have yet to be identified and a genomewide association analysis using DNA chips, microarrays, next-generation sequencers, etc, may also be performed; however, the results will still only be used for the purpose specified in Section 3.7.8.1.1 Objective of DNA Storage.

DNA samples for genomic/genetic analysis will be double-coded at the DNA storage facility and then shipped to the genomic/genetic analysis facility (yet to be determined), where genomic/genetic analysis will be performed under a double-coded condition.

3.7.8.1.5 Informed Consent for DNA Storage

Information for Subjects and ICF for DNA storage and genomic/genetic analysis using stored DNA will be prepared and written informed consent will be obtained from each subject consenting to participate in DNA storage. The date of consent will be recorded on the source documents and eCRF.

If the subject withdraws consent to participate in DNA storage during the DNA storage period, the sponsor will instruct the DNA storage facility to dispose of the subject's DNA sample. The DNA storage facility will then dispose of the DNA sample while maintaining subject anonymity. However, if the subject's sample has become unidentifiable, for example, if information (eg, a code table) that links a DNA sample with subject information has been discarded, the disposal of the DNA sample of the subject who has withdrawn consent may become impossible. However, withdrawal from the trial will not be considered withdrawal of consent for DNA storage. Even if they request their sample(s) to be destroyed, subjects will not lose any benefits, medical treatment, or legal rights which they are allowed. Any results of genomic/genetic analysis obtained prior to the withdrawal of consent will not be disposed of.

3.7.8.1.6 **Disclosure of Genomic/Genetic Analysis Results to Subjects**

Even if genomic/genetic analysis provides some information, such findings would only be exploratory or at an early stage of research, and therefore their scientific reliability and accuracy would not have been fully confirmed. Since disclosure of information the reliability of which has not been scientifically established would be of no benefit to the subjects, the sponsor will not, in principle, disclose the results of genomic/genetic analysis to the subjects.

3.7.9 Other Evaluations

3.7.9.1 **Clinical Global Impression - Severity of Illness**

The investigator or subinvestigator will assess the severity of schizophrenia on the following 8-point scale using the CGI-S at scheduled time points. The date and result of assessment will be recorded on the source documents and eCRF.

0. Not assessed 1. Normal, not at all ill 2. Borderline mentally ill 3. Mildly ill

4. Moderately ill 5. Markedly ill

6. Severely ill

7. Among the most extremely ill patients

3.7.9.2 **Clinical Global Impression - Improvement**

The investigator or subinvestigator will assess the improvement of schizophrenia on the following 8-point scale using the CGI-I at scheduled time points. In Period 1, the current condition of the subject at the start of Period 1 will be assessed and in Period 2 and Period 3 (Cohort 1 and Cohort 1' [as necessary] [single administration period] only), improvement from the start of Period 2 will be assessed. The date and results of assessment will be recorded on the source documents and eCRF.

0. Not assessed	1. Very much improved	2. Much improved	3. Minimally improved
4. No change	5. Minimally worse	6. Much worse	7. Very much worse

3.7.10 End of Trial

The end of trial date is defined as the end date of follow-up of the last subject completing the trial, or if the subject is lost to follow-up, the date of the last contact attempt.

3.8 Procedure for Progression to the Repeated Administration Period (Cohort 2) From the Single Administration Period (Cohort 1 and Cohort 1' [as Necessary])

3.8.1 Criteria for Progression to Cohort 2

The sponsor will determine through discussions, and consultation with the medical expert as necessary, whether or not to progress to the repeated administration period (Cohort 2) based on the results of the PK, safety, and CYP2D6 genotype profiles in the single administration period (Cohort 1 and Cohort 1' [as necessary]).

- 1) PK criteria and procedure for progression to Cohort 2
- Using plasma brexpiprazole concentration data on the conventional tablet and QW formulation from Cohort 1 (single administration period), repeated administration of the 2 mg conventional tablet and the QW formulation at 48 mg will be simulated to ascertain if the dose of 48 mg is appropriate for the OW formulation to be used in Cohort 2 (repeated administration period). If the results of the simulation predict that the QW formulation at 48 mg will produce plasma concentrations far below the trough concentration after repeated dosing of the conventional tablet at 2 mg, then Cohort 1' (single administration period) will be added with the QW formulation at a dose of 54 or 60 mg to assess the safety and tolerability and the doses to be used in Cohort 2 (repeated administration period) will be reassessed. If Cohort 1' (single administration period) is added, a simulation will be performed, and its results will be reviewed in the same manner as in Cohort 1 to ascertain if the selected dose is appropriate for the QW formulation to be used in Cohort 2 (repeated administration period). Conversely, if the results of the simulation predict that the QW formulation at 48 mg will produce plasma concentrations far exceeding the peak concentration after repeated dosing of the conventional tablet at 4 mg, an appropriate dose for repeated administration of the OW formulation will be estimated (36 or 42 mg) based on the results of the simulation and a decision will be made on whether or not to progress to Cohort 2 (repeated administration period). In the event that the sponsor finds it impossible to come to a decision alone, the sponsor will consult the medical expert as necessary and determine through discussions whether or not to progress to Cohort 2 (repeated administration period).

The contents of the discussions will also be recorded.

 Safety criteria and procedure for progression to Cohort 2 If the safety results of the QW formulation in Cohort 1 or Cohort 1' (as necessary) (single administration period) meet any of the following criteria, the sponsor will consult the medical expert and determine through discussions whether or not to progress to the repeated administration period (Cohort 2). The contents of the discussions will also be recorded.

Between dosing of the QW formulation in Period 2 and 14 days after dosing of the QW formulation in Period 3,

- a) At least 1 subject experienced an IMP-related SAE or at least 2 subjects experienced a severe IMP-related AE. Adverse events associated with exacerbation of the underlying disease will be comprehensively assessed through discussions between the medical expert and the sponsor to determine the feasibility of progression to Cohort 2 (repeated administration period).
- b) At least 1 subject experienced IMP-related abnormal blood pressure (systolic blood pressure of < 80 mmHg).
- c) At least 1 subject experienced any of the following IMP-related abnormal ECGs:
 - i) QTc interval (QTcF) of > 500 ms (results at the central ECG laboratory)
 - ii) Prolongation in QTc interval (QTcF) by > 60 ms from baseline (predose in Period 2) (results at the central ECG laboratory)

3.8.2 Doses of Brexpiprazole QW Formulation in the Repeated Administration Period (Cohort 2)

The doses of the QW formulation in Cohort 2 (repeated administration period) may be any of the following depending on the PK results in Cohort 1 and Cohort 1' (as necessary) (single administration period):

- 1) If the results of Cohort 1 (single administration period) with the QW formulation at 48 mg indicate that progression to the repeated administration period (Cohort 2) is appropriate:
- The same subject will receive a single administration of a 2 mg conventional tablet, undergo the washout period, and next receive the first administration of the QW formulation at 24 mg and, subsequently, 4 administrations of the QW formulation at 48 mg.
- 2) If the results of Cohort 1 (single administration period) indicate that the doses need to be changed (based on the results of Cohort 1' [single administration period]):
- A single administration of a 2 mg conventional tablet → washout → the first administration of the QW formulation at 30 mg → 4 administrations of the QW formulation at 60 mg
- A single administration of a 2 mg conventional tablet → washout → the first administration of the QW formulation at 30 mg → 4 administrations of the QW formulation at 54 mg
- 3) If the results of Cohort 1 (single administration period) indicate that the doses need to be changed (based on the results of a simulation):

- A single administration of a 2 mg conventional tablet → washout → the first administration of the QW formulation at 24 mg → 4 administrations of the QW formulation at 42 mg
- A single administration of a 2 mg conventional tablet → washout → the first administration of the QW formulation at 18 mg → 4 administrations of the QW formulation at 36 mg

In the event that CYP2D6 genotype-related dose adjustment of the QW formulation is considered necessary on the basis of the results of Cohort 1 and Cohort 1' (as necessary) (single administration period), the sponsor will determine the doses in the repeated administration period (Cohort 2) after discussions with the medical expert as necessary. The contents/results of the discussions will be recorded.

3.9 Stopping Rules, Withdrawal Criteria, and Procedures

3.9.1 Entire Trial

In the event of sponsor termination or suspension of the trial for any reason, prompt notification will be given to the heads of the trial sites and regulatory authorities in accordance with regulatory requirements.

3.9.2 Individual Site

Individual trial site participation may be discontinued by the sponsor, the investigator, or the IRB if judged to be necessary for medical, safety, regulatory, ethical, or other reasons consistent with applicable laws, regulations, and GCP. The head of the trial site will notify the sponsor promptly if the trial is terminated by the investigator or the IRB at the site.

3.9.3 Individual Subject Discontinuation

3.9.3.1 Treatment Discontinuation

After the first dose of IMP, a subject may stop treatment permanently for a variety of reasons. Treatment discontinuations may be initiated by a subject or may become medically necessary due to AEs, required treatment with a disallowed medication or therapy, or other reasons, as determined by the investigator or subinvestigator. If a subject discontinues treatment, their participation in the trial will be discontinued. Discontinued subjects should be encouraged to complete all ET and follow-up assessments with ET assessments conducted as soon as possible after the subject is withdrawn.

3.9.3.2 Criteria for Withdrawal Before Dose Increase of the QW Formulation

Subjects who meet any of the following criteria after a single administration of the QW formulation in Period 2 of Cohort 1 and Cohort 1' (as necessary) (single administration period) or after the first administration of the QW formulation in Period 2 of Cohort 2 (repeated administration period) will be withdrawn from the trial without dose increase or further administration of the QW formulation.

If, by 2 weeks after a single administration of the QW formulation in Period 2 of Cohort 1 and Cohort 1' (as necessary) (single administration period) or by 1 week after the first administration of the QW formulation in Period 2 of Cohort 2 (repeated administration period):

- 1) Subject experiences either of the following AEs:
- An IMP-related SAE
- A severe IMP-related AE If the event is associated with exacerbation of the underlying disease, the subject can remain in the trial at the discretion of the investigator.
- 2) Subject experiences IMP-related abnormal blood pressure (systolic blood pressure of < 80 mmHg)
- 3) Subject experiences any of the following IMP-related abnormal ECGs:
- QTc interval (QTcF) of > 500 ms
- Prolongation in QTc interval (QTcF) by > 60 ms from baseline (predose in Period 2)
- 4) Subject shows hypersensitivity or allergic reaction to brexpiprazole
- 5) The investigator or subinvestigator judges the subject to be unsuitable for dose increase of the brexpiprazole QW formulation.

3.9.3.3 Documenting Reasons for Discontinuation

All subjects have the right to withdraw and the investigator or subinvestigator can discontinue a subject's participation in the trial at any time if medically necessary. In addition, subjects meeting the following criteria must be withdrawn from the trial. Only one reason for discontinuation (the main reason) can be recorded in the eCRF.

- Adverse event:
 - Continuation of IMP would place the subject at undue risk as determined by the investigator or subinvestigator
 - Safety concern possibly, probably, or likely related to IMP
 - SAE
 - Exacerbation or progression of the underlying disease

- Meeting the criteria for withdrawal before dose increase
- Subject decides to discontinue because of annoyance or discomfort due to a nonserious AE which is not otherwise determined to be an undue hazard
- Subject vomits within 12 hours after IMP administration
- Subject shows allergic reaction or hypersensitivity to brexpiprazole
- Withdrawal of informed consent by the legal representative of the subject
- Withdrawal of informed consent by the subject
- Lost to follow-up
- Pregnancy (see Section 5.5 Pregnancy)
- Investigator's or subinvestigator's decision (other than AE)
- Major protocol deviation
- Termination of all or part of the trial by the sponsor
- Other (record details)

If the subject discontinues IMP due to an AE, the investigator, subinvestigator, or other trial personnel, will make every effort to follow the event until the event is resolved or stabilized, or the subject is lost to follow-up or has died. The procedures in Section 5.7 Follow-up of Adverse Events must be followed.

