3.9.3.4 Withdrawal of Consent

All subjects (and subjects' legal representatives if subjects are minors or are hospitalized for reasons of medical protection) have the right to withdraw their consent from further participation in the trial at any time without prejudice. Subjects (and subjects' legal representatives if subjects are minors or are hospitalized for reasons of medical protection) cannot withdraw consent for use of data already collected as part of the trial, but only for future participation. The investigator or subinvestigator can also discontinue a subject's participation in the trial at any time if medically necessary. Unless the subject (and the subject's legal representative if the subject is a minor or is hospitalized for reasons of medical protection) provides their written withdrawal of consent or there is other written documentation by the investigator or subinvestigator confirming the verbal intent of the subject (and the subject's legal representative if the subject is a minor or is hospitalized for reasons of medical protection) to completely withdraw from the trial, subjects should be followed for all protocol-specified evaluations and assessments, if possible.

Complete withdrawal of consent requires refusal by a subject (and the subject's legal representative if the subject is a minor or is hospitalized for reasons of medical protection) of ALL of the following methods of follow-up (these methods of follow-up will also be noted in the trial ICF):

- Participation in all follow-up procedures specified in the protocol (whether in-clinic, by telephone, or by an in-home visit).
- Participation in a subset of protocol specified follow-up procedures (by a frequency schedule and method, as agreed by subject and staff).
- Contact of the subject by trial personnel, even if only by telephone, to assess current medical condition, and obtain necessary medical or laboratory reports relevant to the trial's objectives.
- Contact of alternative person(s) who have been designated in source records as being available to discuss the subject's medical condition, even if only by telephone, mail, or e-mail (eg, family, spouse, partner, legal representative, friend, neighbor, or physician).
- Access to medical information from alternative sources (eg, hospital/clinic medical records, referring doctor's notes, public records, dialysis, transplantation or vital registries, social media sources).

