Withdrawal of consent is a critical trial event and therefore should be approached with the same degree of importance and care as is used in initially obtaining informed consent. The reasons of a subject (and the subject's legal representative if the subject is a minor or is hospitalized for reasons of medical protection) for an intended withdrawal need to be completely understood, documented, and managed to protect the rights of the subject and the integrity of the trial. A subject (and the subject's legal representative if the subject is a minor or is hospitalized for reasons of medical protection) may initially express their desire to discontinue IMP administration, which is not equivalent to a complete withdrawal of consent for further participation (see Section 3.9.3.1 Treatment Discontinuation). A subject (and the subject's legal representative if the subject is a minor or is hospitalized for reasons of medical protection) may, however, indicate that further trial participation is creating a burden on their work or social schedule. Therefore, the investigator or subinvestigator should follow the procedures outlined in Section 3.9.3.3 Documenting Reasons for Discontinuation to determine if the subject can continue participation in the trial if modifications to his/her treatment and/or schedule of assessments can be accommodated. Only subjects (and subjects' legal representatives if subjects are minors or are hospitalized for reasons of medical protection) who withdraw their permission for all of the above degrees of follow-up are considered to have completely withdrawn their consent to participate in the trial.

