3.9.3.5 Procedures to Encourage Continued Trial Participation

In all cases of impending IMP discontinuation or consent withdrawal, investigators or subinvestigators will be given instructions to meet and discuss with the subject (and the subject's legal representative if the subject is a minor or is hospitalized for reasons of medical protection) their options of continuing in the trial, preferably on therapy. The

investigator or subinvestigator should ensure understanding and documentation of the reasons why the subject (and the subject's legal representative if the subject is a minor or is hospitalized for reasons of medical protection) wishes to withdraw consent.

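### Withdrawal under Section 3.9.3.3 has no exception after the final dose, so it can cut the PK profile short while preventing no dosing (minor, cheap to improve)

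*Protocol*

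**What the plan says.** Protocol 3.9.3.3 introduces its list of triggers with "In addition, subjects meeting the following criteria must be withdrawn from the trial". The list includes an SAE of any causality, a safety concern possibly related to IMP, exacerbation of the underlying disease, allergy, vomiting within 12 hours, pregnancy and a major deviation. It sets no time limit and does not distinguish periods.

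Protocol 3.9.3.1 states: "If a subject discontinues treatment, their participation in the trial will be discontinued". What then remains is described as "Discontinued subjects should be encouraged to complete all ET and follow-up assessments". Under 3.7.6.1.2, PK blood is drawn at the scheduled points or at withdrawal. The ET column of Tables 3.7-1 and 3.7-2 holds one PK sample. The follow-up visit (3.7.3.5) has a physical examination, DIEPSS and AEs, and no PK sample.

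Other text leans the other way. Section 3.9.3.4 says that, absent documented complete withdrawal, "subjects should be followed for all protocol-specified evaluations and assessments, if possible". It describes a subject's "desire to discontinue IMP administration, which is not equivalent to a complete withdrawal of consent for further participation", but refers the reader to 3.9.3.1, which ends participation. Section 3.9.3.5 asks investigators to discuss with subjects "their options of continuing in the trial, preferably on therapy". Section 3.11 defines the trial period regardless of whether every dose is taken. For a significant deviation, 3.14 leaves continuation to a joint decision of investigator and sponsor.

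**The concern.** Before the final dose, withdrawal has an obvious purpose: it stops further drug. After the Period 3 dose, or the fifth Cohort 2 dose, no IMP remains to be withheld. Applied literally, the rule then stops measurement only.

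These are the doses that carry the main PK outputs: AUC∞, CL/F and relative bioavailability in Period 3 (Protocol 6.1.1.2), and AUC168h and CL/F after the fifth dose (6.1.1.3). Missing data are not imputed (7.3), so a subject whose profile is cut short either has no value or has one resting on few terminal points.

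No AUC is at stake earlier. Period 2 of Cohort 1/1' and Cohort 2 doses 1–4 have no AUC parameter, and subjects withdrawn in Period 1 are outside the PK analysis set (7.2.1). In the earlier QW periods, what stops after ET is the scheduled ECG, laboratory, vital-sign and C-SSRS checks while drug is still present.

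Because the text does not rank 3.9.3.3 against 3.9.3.4, two sites could also handle the same event differently.

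**Working it through.** **The plan's own figure.** The only design figure nearby is 20 completers per cohort (3.3.1.1, 7.1). It rests on a simulated probability that is not reported, so it cannot be reproduced. It is not disputed here.

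**Samples lost.** The planned profile after the last dose is "A total of 11 time points, namely, predose and 3, 9, 24, 36, 48, 72, 120, 168, 240, and 312 hours postdose". Counting the points after each stop time:

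| Last draw | Scheduled samples remaining | Terminal points from 36 h on |
|---|---|---|
| 48 h | 5 | 2 |
| 72 h | 4 | 3 |
| 120 h | 3 | 4 |
| 168 h | 2 | 5 |
| 312 h (plan) | 0 | 7 |

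One ET sample replaces whatever remains. For comparison, 3.7.6.1.2 says of the half-life in earlier conventional-tablet trials, "which was determined at 3 to 8 time points between 36 to 312 hours postdose".

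**Model inputs.** Half-life 71.5 h and median tmax of about 30 h for the QW-A formulation (Table 1.2-2). Assumed: one compartment, 2 h lag, zero-order input over 28 h, so input ends at 30 h. Sensitivity half-lives are 52.9 h (lowest mean in 3.7.6.1.2) and 106.8 h (highest in 1.2.2.1).

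**Share of AUC∞ observed by time t (after input ends).** With k = ln 2/71.5 = 0.00969 per h and T = 28 h:

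share = 1 − [(e^{kT} − 1)/(kT)] × e^{−k(t−2)}

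The bracket is (e^{0.2714} − 1)/0.2714 = 1.149.

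- 48 h: 1 − 1.149 × 0.640 = 26%
- 72 h: 1 − 1.149 × 0.507 = 42%
- 120 h and 168 h, same formula: 63% and 77%
- 312 h: 1 − 1.149 × 0.0495 = 94%

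At 72 h the range over half-lives 52.9 to 106.8 h is 52% to 30%. For AUC168h after the fifth dose (24, 48, 48, 48, 48 mg weekly), superposition of the same curve gives 37%, 56% and 83% observed by 48, 72 and 120 h.

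**Reliability of one subject's AUC∞.** Simulation of 100,000 subjects with lognormal error per sample, the linear trapezoid and unweighted log-linear regression as in SAP 10.2, and all points from 36 h used for λz (assumed). Shown is the share off by more than 20% or not estimable:

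| Stop | 10% error | 20% error |
|---|---|---|
| 48 h, no ET sample | 82% | 91% |
| 48 h, plus ET at 60 h (assumed) | 63% | 80% |
| 72 h, no ET sample | 45% | about 70% |
| 72 h, plus ET at 96 h (assumed) | 16% | 44% |
| 120 h, no ET sample | 6% | 29% |
| 168 h, no ET sample | <1% | 8–10% |
| 312 h (plan) | <1% | 1–2% |

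Over the two sensitivity half-lives, the no-ET figures at 10% error run from 74% to 89% (48 h) and 26% to 65% (72 h).

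**AUC168h, fifth dose, no ET sample, 10% error** (extrapolated to 168 h with the fitted slope, an assumption): off by more than 20% in 61% at 48 h, 7% at 72 h, and under 1% at 120 h.

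**Mean AUC.** 200,000 simulated cohorts of 21 or 22 subjects, with 1 or 2 lost and 20 left. If loss is unrelated to exposure, the ratio to the true mean is 1.00. In the worst case, losing the 1 or 2 highest exposures lowers the mean by 11% or 17% at CV 78% (5360/6840 from Table 1.2-2), or by 5% or 8% at an assumed CV of 40%. The standard error of a 20-subject mean is 0.78/√20 = 17% or 0.40/√20 = 9%.

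**The case against.** **The sections can be read together.** Section 3.9.3.4 concerns consent and says follow-up is only if possible. For a discontinued subject, ET and follow-up could be taken as the specified evaluations. A reader might infer a flat contradiction, but the documents support only an ambiguity. The sentence in 3.9.3.1 is also tied to stopping treatment, so it does not clearly reach a subject who has already had every dose. That leaves 3.9.3.3 as the operative rule.

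**Removal is not always automatic.** Section 3.14 covers deviations. Section 3.9.3.2 lets the investigator retain a subject with an exacerbation-related event, though only before the dose increase. Neither helps after the final dose for an SAE, a related safety concern or an exacerbation.

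**Withdrawal has a second function.** The restrictions in 4.1–4.4 end at the last scheduled assessment or on completion of ET. Early ET therefore frees a subject with an allergic reaction or psychotic exacerbation from the bans on adrenaline, clozapine, interacting drugs and ECT, and from the antipsychotic dose cap. This stands in full, and any fix must preserve it.

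**The ET sample recovers information.** Under SAP 10.2, an out-of-window sample still enters parameter calculation, at its actual time. This stands. It is why the ET rows are shown, and the reported AUC_%Extrap also flags a heavily extrapolated value.

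**The consequence is small.** Analyses are descriptive, the target counts completers, dose selection for Cohort 2 uses simulation from concentration data, and subjects who vomit within 12 hours are excluded from the PK set anyway. All of this stands and limits the point to minor.

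**Conclusion.** The point holds as a cheap, minor improvement. The plan as written discards already scheduled PK and safety data after the final dose while preventing no dosing. It matters mainly when sampling stops within 2–3 days of that dose. One subject's AUC∞ then fails the 20% criterion in about 82% (48 h) or 45% (72 h) of cases without an ET sample, or about 63% or 16% with one at 60 h or 96 h. By 168 h the loss is slight. These figures rest on the assumed one-compartment release model, 10% error, the λz window and the ET times. The number of subjects affected is unknown and probably small.

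Three stronger readings are not supported:

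- *Mean AUC will be biased downwards.* That needs withdrawal to track exposure, which nothing establishes. Schizophrenia was the most frequent AE leading to discontinuation in the Japanese long-term trial (1.2.2.5). In the Japanese multiple-dose trial (1.2.2.3), the two schizophrenia SAEs that led to discontinuation were at 1 mg and 4 mg. Even the worst case is within about one standard error.
- *The sample size is undermined.* The target of 20 counts completers, so withdrawn subjects do not use it up.
- *Withdrawn subjects go unmonitored.* ET, the follow-up visit and follow-up of the causative AE all remain.

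**What to change.** Keep every trigger. In 3.9.3.3, with a conforming change to the participation sentence in 3.9.3.1, state that:

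- meeting a criterion ends further IMP dosing;
- where the subject agrees and it is medically appropriate and feasible, the PK and safety assessments already scheduled for the last dose received continue through Day 14 after that dose (for Cohort 2 doses 1–4, those listed for that dose);
- otherwise the ET set is used.

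In 4.1–4.4, add that the medication, therapy and dietary restrictions end for that subject when the trigger is met, so that needed treatment is never delayed.

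PK sampling may stop after vomiting within 12 hours, or after use of a CYP2D6/CYP3A4 inhibitor or inducer. Such subjects, or the concentrations after such use, are already excluded by Protocol 7.2.1 and SAP 10.2 respectively. Safety assessments continue.

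The cost is a few already designed visits or samples for subjects who stop early, plus short edits to 3.9.3.1, 3.9.3.3 and 4.1–4.4. The most valuable samples, those in the first 5 days, fall inside the planned inpatient stay (Days 1–8 of Period 3; Days 29–36 of Cohort 2 Period 2).
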